8.4 Serious Adverse Event Reporting (SAE)

An adverse event or suspected adverse reaction is considered “serious” if, in the view of either the investigator or the sponsor, it results in any of the following outcomes:

- Death
- A life-threatening adverse drug experience – any adverse experience that places the patient, in the view of the initial reporter, at immediate risk of death from the adverse experience as it occurred. It does not include an adverse experience that, had it occurred in a more severe form, might have caused death.
- Inpatient hospitalization or prolongation of existing hospitalization
- A persistent or significant incapacity or substantial disruption of the ability to conduct normal life functions.
- A congenital anomaly/birth defect.
- Pregnancy
- Overdose of investigational agent
- Onset of a new secondary malignancy while on study.

Important medical events that may not result in death, be life-threatening, or require hospitalization may be considered a serious adverse drug experience when, based

upon appropriate medical judgment, they may jeopardize the patient or subject and may require medical or surgical intervention to prevent one of the outcomes listed in this definition. Examples of such medical events include allergic bronchospasm requiring intensive treatment in an emergency room or at home, blood dyscrasias or convulsions that do not result in inpatient hospitalization, or the development of drug dependency or drug abuse (21 CFR 312.32).

- Important medical events as defined above, may also be considered serious adverse events. Any important medical event can and should be reported as an SAE if deemed appropriate by the Principal Investigator or the IND Sponsor, IND Office.
- All events occurring during the conduct of a protocol and meeting the definition of a SAE must be reported to the IRB in accordance with the timeframes and procedures outlined in “The University of Texas M. D. Anderson Cancer Center Institutional Review Board Policy for Investigators on Reporting Unanticipated Adverse Events for Drugs and Devices”. Unless stated otherwise in the protocol, all SAEs, expected or unexpected, must be reported to the IND Office, regardless of attribution (within 5 working days of knowledge of the event).
- **All life-threatening or fatal events**, that are unexpected, and related to the study drug, must have a written report submitted within **24 hours** (next working day) of knowledge of the event to the Safety Project Manager in the IND Office.
- Unless otherwise noted, the electronic SAE application (eSAE) will be utilized for safety reporting to the IND Office and MDACC IRB.
- Serious adverse events will be captured from the time of the first protocol-specific intervention, until 30 days after the last dose of drug, unless the participant withdraws consent. Serious adverse events must be followed until clinical recovery is complete and laboratory tests have returned to baseline, progression of the event has stabilized, or there has been acceptable resolution of the event.
- Additionally, any serious adverse events that occur after the 30 day time period that are related to the study treatment must be reported to the IND Office. This may include the development of a secondary malignancy.

Reporting to FDA:

- Serious adverse events will be forwarded to FDA by the IND Sponsor (Safety Project Manager IND Office) according to 21 CFR 312.32.

It is the responsibility of the PI and the research team to ensure serious adverse

events are reported according to the Code of Federal Regulations, Good Clinical Practices, the protocol guidelines, the sponsor's guidelines, and Institutional Review Board policy.

Investigator Communication with Supporting Company:

Serious adverse event will be reported by FAX concurrently to Bristol-Myers Squibb (BMS) ([contact]) or BMS email: [contact]. Information not available at the time of the initial report (e.g., an end date for the adverse event or laboratory values received after the report) must be documented on a follow-up report. A final report to document resolution of the SAE is required. Hospitalizations for the management of any expected adverse events (previously described) should be reported to BMS within 5 business days of the event.

Pregnancies: Any pregnancy that occurs during study participation or within 4 weeks of the patient's last study drug administration should be reported to Bristol-Myers Squibb within 24 hours of learning of its occurrence.

The Investigator will follow the pregnant female until completion of the pregnancy. The Investigator will provide this information as a follow-up to the initial SAE.

If the outcome of the pregnancy meets the criteria for immediate classification as a SAE (i.e., spontaneous abortion [any congenital anomaly detected in an aborted fetus is to be documented], stillbirth, neonatal death, or congenital anomaly), the Investigator should follow the procedures for Expedited Reporting of SAEs.

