3.0 STUDY POPULATION

3.1 Inclusion Criteria

1. Patients with AML in remission (defined as CR, CR with incomplete platelet recovery –CRp-, CR with incomplete hematologic recovery -CRi-, or partial remission defined as a bone marrow with <10% blasts after therapy with or without hematologic recovery).
2. High risk for relapse defined as:
 - a. 1st CR with high risk features for relapse (including history of prior malignancy treated with chemotherapy or radiotherapy, or history of myelodysplastic syndrome, myeloproliferative disorder, chronic myelomonocytic leukemia, MDS/MPN or other hematologic malignancy thought to have evolved to AML [i.e., secondary AML, sAML]; high risk cytogenetics at diagnosis; FLT3 mutated at diagnosis; or presence or minimal residual disease assessed by PCR, cytogenetics, and/or flow cytometry at time of enrollment)
 - b. 2nd CR regardless of disease characteristics at the time of diagnosis.
3. Have received induction chemotherapy and at least one cycle of consolidation chemotherapy. Patients should have achieved a CR within 12 months of enrollment onto protocol.
4. No further chemotherapy or SCT planned at the time of enrollment.
5. Age 18 years or older.
6. Adequate organ function: creatinine \leq 1.5 x ULN; serum bilirubin \leq 1.5 x ULN; AST and ALT \leq 2.5 x ULN.
7. ECOG performance status \leq 2
8. Females of childbearing potential must have a negative serum or urine beta human chorionic gonadotrophin (β -hCG) pregnancy test result within 24 hours prior to the first dose of treatment and must agree to use an effective contraception method during the study and for 23 weeks after the last dose of the study drug. Females of non-childbearing potential are those who are postmenopausal greater than 1 year or who have had a bilateral tubal ligation or hysterectomy.

9. Males who have partners of childbearing potential must agree to use an effective contraceptive method during the study and for 31 weeks following the last dose of study drug
10. Patients or their legally authorized representative must provide written informed consent.

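### The pregnancy reporting window in section 8.4 is not aligned with the contraception periods in section 3.1: between 0 and 19 of 23 weeks (women) and between about 5 and 27 of 31 weeks (men's partners) are uncovered, depending on how study participation is read

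*Combined protocol and SAP*

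**What the plan says.** Section 3.1 sets the contraception conditions. Under item 8, women of childbearing potential "must agree to use an effective contraception method during the study and for 23 weeks after the last dose of the study drug". Under item 9, men whose partners could become pregnant "must agree to use an effective contraceptive method during the study and for 31 weeks following the last dose of study drug".

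Section 8.4, in the part on communication with the supporting company, sets the notification rule. It covers "Any pregnancy that occurs during study participation or within 4 weeks", counted from the last dose, and the site has 24 hours to notify the company once it knows. The investigator then follows the pregnant woman to the end of the pregnancy, and adverse outcomes go through expedited reporting. Neither of those sentences sets a longer window, and neither mentions partners of male patients.

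Section 8.4 also lists pregnancy among the serious adverse events (SAEs). The general capture period is: "Serious adverse events will be captured from the time of the first protocol-specific intervention, until 30 days after the last dose of drug". A narrower rule applies later, with reports going to the IND Office: "any serious adverse events that occur after the 30 day time period that are related to the study treatment must be reported to the IND".

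Section 9.0 plans a further 6 months of follow-up after treatment on protocol is completed. It also expects that 25% of patients may become eligible for transplant and may leave the study. Section 4.2.3 requires removal from the study on confirmed, clinically significant hematologic relapse.

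**The concern.** Sections 3.1 and 8.4 both count from the last dose but use different lengths. For 23 or 31 weeks the protocol asks patients to avoid conception, yet the only post-dose period named for pregnancy notification is 4 weeks. A pregnancy conceived after week 4, while contraception is still required, could go unreported and its outcome might not be followed. That would be a gap in maternal and fetal safety information.

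Scheduled contact offers little backup. Section 6.2 ends adverse event assessment about 30 days after therapy, and neither 6.2 nor 6.3 lists a pregnancy test. The reporting sentence is therefore the main safeguard.

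**Working it through.** The plan states no derived figure to reproduce. The check compares windows, all measured from the last dose.

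**Inputs**
- Contraception period C: 23 weeks for women (section 3.1, item 8); 31 weeks for men (section 3.1, item 9).
- Explicit pregnancy window: 4 weeks (section 8.4).
- General SAE window: 30 days (section 8.4), so 30 / 7 = 4.29 weeks.
- Follow-up after treatment: 6 months (section 9.0), so 6 × 365.25 / 12 / 7 = 26.09 weeks. This treats the follow-up as starting at the last dose, which is an assumption.

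**Formula:** for a reporting window W, uncovered weeks = max(0, C − W), and uncovered share = uncovered weeks / C.

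| Reading of the reporting window | Women (C = 23) | Men's partners (C = 31) |
|---|---|---|
| Participation ends with treatment or on early exit; W = 4 | 23 − 4 = 19 weeks; 19/23 = 82.6% | 31 − 4 = 27 weeks; 27/31 = 87.1% |
| SAE route; W = 4.29 | 23 − 4.29 = 18.71 weeks; 81.4% | 31 − 4.29 = 26.71 weeks; 86.2% |
| 6-month follow-up counts as participation; W = 26.09 | 0 weeks; 0% | 31 − 26.09 = 4.91 weeks; 15.8% |

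The SAE route adds 2 days (30 against 28). The third row applies only to patients who stay on study through the follow-up. For a patient removed for relapse, or off study for transplant, participation may already have ended, and the first row applies again.

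If the reporting window equalled the contraception period, the uncovered time would be 0 weeks for both groups under every reading.

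**The case against.** The strongest reply is that the reporting rule has two limbs, and the 4-week limb is only one of them. Section 9.0 describes the 6-month follow-up and then, in the next sentence, speaks of patients coming off study, which supports counting those months as participation. On that reading a woman who completes treatment is covered throughout her 23 weeks. The 4-week limb would still have a purpose, as a minimum for patients who leave early. This stands as a possible reading, and it is why 83% and 87% cannot be given as the only answer. It does not remove the problem: the term is undefined, early leavers still have only 4 weeks, and a gap of about 5 weeks for men's partners remains even for patients who complete treatment.

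A reader might also infer that a late pregnancy would simply not be reported or followed. The documents do not support that. Pregnancy and birth defects are both listed as SAEs, SAEs arising during the conduct of the protocol go to the IRB, and treatment-related SAEs after day 30 go to the IND Office with no stated end date. A birth defect judged related would therefore be reportable. What these routes do not do is reliably capture a late pregnancy as an exposure, because a judgement of relatedness stands in the way.

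Two smaller points are fair. The rule covers any pregnancy and excludes nobody, so partner pregnancies are unmentioned rather than ruled out. And section 3.1 never calls 23 or 31 weeks a risk period: a contraception condition and a notification window are separate duties, and a site can comply with both as written. That they should match is an inference from their shared purpose.

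**Conclusion.** The two sections are not aligned, and the explicit window, followed as written, can miss pregnancies conceived while the protocol still requires contraception. The uncovered time is 19 of 23 weeks (83%) for women and 27 of 31 weeks (87%) for men's partners if participation ends with treatment or the patient leaves early. It is 0 weeks and about 5 of 31 weeks (16%) if the 6-month follow-up counts as participation and the patient stays for it.

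A flat statement that pregnancies are reportable only up to 4 weeks after the last dose would go too far, because it drops the participation limb of the rule. The percentages are shares of calendar time, not expected numbers of missed pregnancies. With at most 30 patients, few pregnancies are likely, though the documents give no rate from which to estimate a number. The primary endpoint, the futility and toxicity rules and the analysis are unaffected. This is a safety-reporting inconsistency that should be corrected because the correction is cheap.

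**What to change.** Reconcile section 8.4 with section 3.1. Pregnancy reporting and outcome follow-up should cover the whole post-dose period for which the protocol requires contraception, whether or not the patient is still on study. State expressly that pregnancies in partners of male patients are included. Define study participation, and say whether it includes the 6-month follow-up in section 9.0. This review takes no position on how long contraception should last; the reporting window should follow whatever period the protocol sets.

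The cost is a short edit to section 8.4 and a longer period of passive reporting. No added visit or test is needed, and nothing in the statistical design changes.

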9.0 STATISTICAL CONSIDERATIONS

This is a phase II study of Nivolumumab as a maintenance therapy in patients with high risk AML and in first or second remission. The primary objective is to assess the recurrence-free survival rate at 6 months. It is expected the median RFS under the treatment is at least 8 months. Assume that RFS time follows an exponential distribution, the RFS rate at 6 months will be 59.5%. A maximum of 30 patients will be enrolled, and the study will monitor both futility and toxicity.

Futility monitoring

The study will be continuously monitoring RFS for futility, using the method of Thall, Wooten, and Tannir (2005). It is assumed that the RFS time is exponentially distributed with a median of λ_E among patients who receive nivolumumab as a maintenance therapy, and a median of λ_H is assumed for the historical treatment. Further, we assume that λ_H follows an inverse gamma distribution, i.e., $\lambda_H \sim IG(3.6, 20.8)$, which has a mean of 8 months and variance of 40. To reflect the little prior knowledge of λ_E we assume an inverse gamma prior distribution with the same mean of 8 months and a much larger variance of 500, i.e., $\lambda_E \sim IG(2.128, 9.024)$. The trial will be stopped early if $Pr(\lambda_E > \lambda_H | \text{data}) < pL$, where $pL=0.25$. That is, the study will be stopped if at any time during the study the data suggest that there is less than 25% probability that the median RFS was

longer than that in the historical data. This futility monitoring rule will be first applied when 10 patients have been enrolled. A maximum of 30 patients will be enrolled into this study at an expected accrual rate of 2-3 patients per month. From historical experience, 25% of patients in this cohort may become eligible for stem cell transplant and may come off study. For purposes of this analysis, these patients will be censored at the time of receiving transplant. Patients will be followed up for an additional 6 months after completing treatment on protocol. Once these patients come off of study, they will be followed on a leukemia department long-term follow-up protocol and will not be receiving the evaluations described in section 6.2. The trial will be conducted using the Clinical Trial Conduct (CTC) website maintained by the Department of Biostatistics at MDACC. The website will be programmed with the operating characteristics of the Bayesian design of this protocol to allow continuous monitoring for futility.

The operating characteristics of the design, based on an overall assumed accrual rate of 2.5 patients per month and an additional follow-up of 6 months with 5000 simulated trials per scenario, are given in the following table. OneArmTTE (version 2.2) was used for the design and simulation.

Scenario	True Median (months)	True RFS rate at 6 months	Pr(Stopped Early)	Mean No. patients (25%, 75%)	Average Trial Duration (months)
1	2	12.50%	1	10.5 (10, 10)	4.24
2	4	35.40%	0.86	16.7 (10, 23)	7.83
3	6	50%	0.36	24.1 (14, 30)	13.56
4	8	59.50%	0.16	27.2 (30, 30)	16.01
5	10	66%	0.08	28.6 (30, 30)	16.98
6	12	70.70%	0.04	29.2 (30, 30)	17.4

Toxicity monitoring

In addition, we will continuously monitor treatment-related toxicities using the Bayesian approach of Thall, Simon, Estey (1995). Specifically, the trial will be stopped if $\text{Prob}(\pi_T > 0.30 | \text{data}) > 0.88$, where π_T is the toxicity rate and we assume a beta (0.6, 1.4) prior for π_T . That is, if at any given time, there is more than 88% probability that the toxicity rate of the maintenance therapy with nivolumab is greater than 30%, the trial will be stopped. For the purpose of toxicity monitoring, toxicities are defined as any treatment –related clinically significant \geq grade 3 non-hematologic AEs occurred any time during the trial. We will apply this stopping rule starting from the 10th patient. The stopping boundaries corresponding to this toxicity monitoring rule are described in the following table:

Stopping boundaries for treatment-related grade 3, 4 non-hematologic toxicities

The number of patients evaluated for toxicities	10 -12	13-15	16-18	19-20	21-23	24-26	27-29
Stop the trial if greater than or equal to this many of patients with toxicities	6	7	8	9	10	11	12

The operating characteristics for toxicity monitoring are described in the following table. MultcLean Desktop 2.1.0 was used for the design and simulations for toxicity monitoring.

Operating characteristics for Toxicity Monitoring

True Toxicity Rate	Early Stopping Probability	Sample Size		
		25 th percentile	Median	75 th percentile
0.1	0.0007	30	30	30
0.2	0.0353	30	30	30
0.3	0.2447	29	30	30
0.4	0.635	11	18	30
0.5	0.9134	10	11	15

A toxicity summary will be submitted to the IND medical monitor after every 3 patients starting from the 10th patient.

For the primary analysis of the efficacy endpoint, we will use Kaplan-Meier methodology to compute the RFS rate at 6 months and the 95% confidence interval. As a secondary analysis, we will perform a competing risk analysis treating stem cell transplant as a competing event for RFS." . The Kaplan-Meier method will be used to estimate the median RFS time and the probability of overall survival. Expressions of immune mediated markers will be summarized with descriptive statistics: means medians, ranges, and standard deviations. Two-sample t test or Wilcoxon rank sum test will be used to compare the expressions of markers between patients remaining in CR and patients having recurrence disease. Scatterplots will be used to explore possible associations between clinical responses and the immunomodulatory markers. Spearman correlation coefficients will be computed to evaluate the association between MRD and immunomodulatory markers, as well as the association between MRD and the changes in marker expressions pre and post treatment.

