Current standard of care in AML features induction chemotherapy followed by consolidation strategy (chemotherapy versus stem cell transplantation in selected patient populations). At the conclusion of induction and consolidation, there is yet no standard of care for “maintenance” strategies, especially in those subgroups of AML patients demonstrating a particularly high risk of relapse (e.g. FLT3-ITD mutated patients, high risk cytogenetics (monosomies of either chromosome 5 or 7 or complex cytogenetics), secondary or treatment-related AML, or those in 2nd CR). This subgroup of patients is at very high risk of relapse with no current standard treatment options except active surveillance once therapy for induction and consolidation has been completed. Review of our own experience shows that the RFS of frontline patients with high risk features is similar to any patient with AML who in their second CR (ie. relapsed after frontline therapy), suggesting that these groups can be studied together.

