hypoproliferation and decreased production of cytokines, has been characterized in solid tumors¹² and, more recently, in AML animal models.¹³ These lymphocytes are characterized by the co-expression of Tim-3 and PD-1 on CD8+ T-cells that are deficient in their ability to produce a cytokine response in response to PDL1-expressing AML cells. Several studies have suggested that PD-1 blockade can enhance recruitment of effector T-cells and produce therapeutic anti-cancer immunity.^{14,15} Recently, the use of an anti-PD-1 antibody (lambrolizumab) was reported to induce response in 38% of patients with advanced melanoma (52% among those treated at the highest tolerated dose)¹⁶.

Nivolumab (BMS-936558, MDX-1106) is a fully human immunoglobulin G4 (IgG4) monoclonal anti-PD-1 antibody that, upon binding to PD-1, prevents its interaction with its ligands PDL1 and PDL2. Studies in melanoma have shown evidence of clinical activity with a favorable toxicity profile. Among 90 patients with advanced melanoma treated with nivolumab in a phase 1 study, 25% responded, with responses observed in both ipilimumab-naïve and ipilimumab-exposed patients.¹⁷

In this study we propose to investigate the role of nivolumab in treating patients with AML in CR at high risk for relapse to determine whether treatment with this anti-PD-1 antibody may prevent AML relapse.

2.4 Anti-PD1 (Nivolumab, BMS-936558, MDX1106):

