2.6 Rationale for the proposed study

Despite the high rate of remission in AML, most patients relapse. Continuation of chemotherapy does not only expose the patient to increasing risks for adverse events but is also ineffective. The only approach for maintenance in AML that has been demonstrated to be beneficial in a randomized trial is immunotherapy with interleukin-2 with histamine. We hypothesize that by using nivolumab as maintenance therapy we will induce an immune response that will be able to reduce the risk of

relapse in patients at high risk. We thus propose to investigate the role of nivolumab in treating patients with AML in CR at high risk for relapse to determine whether treatment with this anti-PD-1 antibody may prevent AML relapse. If this study suggests a decreased rate of relapse and adequate safety, we would proceed then to a randomized trial to confirm the observation with focus on specific subsets as individual categories (e.g., FLT3 mutated, secondary leukemias, etc).

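### Does section 9.0 need an efficacy target and a final success criterion beyond its futility rule?

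*Combined protocol and SAP*

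**What the plan says.** Sections 1.1 and 9.0 both give the primary objective as evaluating or assessing the RFS rate at 6 months. For the primary analysis, section 9.0 says "we will use Kaplan-Meier methodology to compute the RFS rate at 6 months and the 95% confidence interval". It gives no reference value, alpha or power.

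On the expected effect, section 9.0 says "It is expected the median RFS under the treatment is at least 8 months", which it converts to 59.5% at 6 months under an exponential model. The historical median has an inverse gamma prior, IG(3.6, 20.8), "which has a mean of 8 months and variance of 40". The nivolumab median has a prior with the same mean and variance 500. The trial stops if the posterior probability that the nivolumab median exceeds the historical one falls below 0.25, checked from the tenth patient. There is no upper cutoff.

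The wider aim is in the background. Section 2.0 proposes the study "to determine whether treatment with this anti-PD-1 antibody may prevent AML relapse". Section 2.6 adds: "If this study suggests a decreased rate of relapse and adequate safety, we would proceed then to a randomized trial". Section 2.0 also says "Review of our own experience shows that the RFS of frontline patients with high risk features is similar to any patient with AML" in second remission, without a figure.

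**The concern.** Sections 2.0 and 2.6 speak of preventing or decreasing relapse, and section 2.6 attaches a consequence to that finding. A reader then looks in section 9.0 for the result that would count as a decrease and does not find one. The expected median equals the historical prior mean, so no improvement is named. The medians of 10 and 12 months in the operating-characteristics table are only simulation scenarios. Toxicity, by contrast, has an explicit reference rate (30%) and cutoff (0.88).

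If this mattered, the harm would be a benchmark chosen after the data are seen. The same result could be called encouraging or not, and patients might be committed to a randomized trial on that reading. Someone might also take completion without a futility stop as evidence of activity, which it is not.

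**Working it through.** **Inputs (all section 9.0).** Exponential RFS; λ_H ~ IG(3.6, 20.8); λ_E ~ IG(2.128, 9.024); stop if Pr(λ_E > λ_H | data) < 0.25; first look at 10 patients; maximum 30; 2.5 patients per month; 6 months of further follow-up.

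**1. The plan's own figures reproduce.**
- RFS at 6 months = 2^(−6/median). For a median of 8: 2^(−0.75) = 59.5%.
- Inverse gamma mean = b/(a−1): 20.8/2.6 = 8 and 9.024/1.128 = 8. Variance = mean²/(a−2): 64/1.6 = 40 and 64/0.128 = 500.
- With d events and total follow-up T, λ_E | data ~ IG(2.128 + d, 9.024 + ln2·T). Then Pr(λ_E > λ_H | data) = 1 − F(x), where F is the Beta(3.6, 2.128 + d) distribution function and x = 20.8/(20.8 + 9.024 + ln2·T).
- Simulation with 40,000 trials per scenario:

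| True median (months) | 2 | 4 | 6 | 8 | 10 | 12 |
|---|---|---|---|---|---|---|
| Stop, protocol | 1 | 0.86 | 0.36 | 0.16 | 0.08 | 0.04 |
| Stop, recomputed | 1.00 | 0.853 | 0.365 | 0.152 | 0.076 | 0.042 |

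**2. What completion means.** From the protocol's table, 1 − 0.16 = 84% of trials are not stopped at a true median of 8 months, and 1 − 0.36 = 64% at 6. Solving Pr(λ_E > λ_H | data) = 0.25 gives an observed exponential median of 4.23 months with 15 events and 4.29 with 20. The rule screens out poor results; it does not identify good ones.

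**3. Is the comparator undefined?** IG(3.6, 20.8) has mean 8 but median 6.36, with 66% of its mass below 8. Take an observed median of 8 months with 20 events, so ln2·T = 8 × 20 = 160 and λ_E | data ~ IG(22.128, 169.024). The probability of improvement is then:
- 0.63 against λ_H, the comparator the plan uses;
- 0.44 against a fixed 8 months;
- 0.83 against a fixed 6.36 months.

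The spread is genuine, but only the first comparison is in the plan. Section 9.0 proposes no fixed point as comparator.

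**4. Precision of the primary estimate.** Suppose 18 of 30 are event-free at 6 months with no earlier censoring. The standard error is √(0.6 × 0.4/30) = 0.0894. The plain 95% interval is 42.5–77.5% and the log-log interval 40.5–75.0%. As exponential medians the log-log interval is about 4.6–14.4 months. The interval is valid but wide.

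**5. What a final rule would buy.** The cutoffs below are illustrations and are not in the plan. Entries are the share of trials not stopped for futility that also pass the final cutoff.

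| True median (months) | 8 | 10 | 12 | 16 |
|---|---|---|---|---|
| Pr > 0.80, final look 6 months after last entry | 6% | 28% | 55% | 87% |
| Same, about 25% transplant censoring (assumed 0.04/month) | 7% | 27% | 52% | 83% |
| Pr > 0.80, final look 12 months after last entry | 5% | 28% | 58% | 91% |
| Pr > 0.70, final look 6 months after last entry | 27% | 61% | 83% | 97% |

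Two final looks are shown because section 9.0 says "Patients will be followed up for an additional 6 months after completing treatment on protocol" in the text but simulates "an additional follow-up of 6 months with 5000 simulated trials per scenario". The choice barely moves the result.

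Passing 0.80 needs an observed median of about 11.5 months with 15 events or 11.3 with 20. Because λ_H is never updated, even unlimited data give only 0.66, 0.78 and 0.85 at true medians of 8, 10 and 12.

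An exact binomial test against 59.5%, with all 30 evaluable, does no better. Requiring at least 23/30 has one-sided alpha 0.039 and power 0.15 at 66% (median 10) and 0.31 at 70.7% (median 12).

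**The case for a change.** The strongest case for a change is that no section says the study is estimation only, while sections 2.0 and 2.6 promise more than an estimate. If the benchmark is picked afterwards, the reading can flip. With a 0.80 cutoff, 43%, 52% and 38% of trials at true medians of 8, 10 and 12 months would pass against a fixed 6.36 but fail against λ_H. Two or three sentences would prevent that and would add no patients.

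Part of this stands. Section 9.0 names no target above 8 months and no final cutoff, so the efficacy half of the section 2.6 condition is left to judgement. Completing the trial is not in itself evidence of benefit.

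The rest does not carry. The flip rates depend on a cutoff and a fixed benchmark that the plan does not contain, and a fixed point will naturally disagree with a wide prior. The wording about preventing relapse is background. The objective stated in sections 1.1 and 9.0 is a rate, and the analysis gives it. Section 2.6 describes a later programme decision that also weighs safety, and it leaves confirmation to the randomized trial. The proposed sentences would only write down what the design already is, and no analysis or result would differ.

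**Conclusion.** No change follows. The absence of a success rule is a fair trade-off for a single-arm phase II study of at most 30 patients, designed to estimate a 6-month rate with futility and toxicity stops. The stated figures are correct, the estimate is not biased by the omission, and safety is unaffected.

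A binding rule would force a choice between a strict cutoff that misses most moderately better treatments (0.80 passes 28% at a true median of 10 months) and a lenient one that passes 27% at the historical prior mean (0.70 at 8 months). Reasonable statisticians would differ on that choice. Analysts can report the Kaplan-Meier rate with its interval and, if they want a summary against history, the final Pr(λ_E > λ_H | data) against the prior already specified. They should not present completion as success.

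The figures rest on the protocol's exponential model and accrual of 2.5 per month. The cutoffs, the timing of transplant censoring and the 18/30 example are assumptions made for illustration.
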